5.3 DATA ANALYSIS GENERAL CONSIDERATIONS

5.3.1 Pooling of Centers

This is a multi-center, international study conducted in three geographic regions, i.e. United States, Europe, and Asia. Data from the centers in the same region and age group will be pooled together for analysis purposes. Each of these strata should have at least 6 subjects. If there are strata with <6 subjects then age-groups will be combined within the region.

For analyses by country, if there are countries with <6 subjects then the countries will be sorted in descending order by the number of subjects in each geographic region. Starting from the smallest, countries will be pooled until the criteria of 6 subjects is fulfilled or there is no country of size <6 left to be pooled in that geographic region. If there is no country of size <6 left to be pooled but the current country is of size <6 then the current country will be pooled with the next country in that geographic region in the order.

5.3.2 Adjustments for Covariates

The Prerandomization Phase seizure frequency per 28 days value will be used as a covariate, and region and age group will be used as a factor in the efficacy models for the primary analysis. Additional covariates may also be explored.

5.3.3 Multiple Comparisons/Multiplicity

If the primary endpoint is statistically significant then the 3 key secondary efficacy endpoints will be tested in a sequential manner.

Median percent change in total seizure frequency per 28 days during double -blind treatment will be tested first. If this test is significant at 0.05 level, then the 50% responder rate in the Maintenance Period for drop seizures will be tested. If this is significant then the 50% responder rate in the Maintenance Period for total seizures will be tested. All tests will be at a 2 -sided 0.05 significance level.

5.3.4 Examination of Subgroups

The following endpoints will be summarised by age (2-<12, 12-<18, 18-<65, ≥65):

Disposition; demography; epilepsy-specific medical history, number of baseline AEDs, baseline AEDs, compliance, percent change in drop, non-drop and total seizure frequency, 50%/75% response and seizure freedom rates in drop, non-drop and total seizures; clinical global impression exposure; treatment-emergent adverse events; change from baseline in laboratory values; treatment-emergent markedly abnormal laboratory values; change from baseline in vital signs; and Columbia Suicide Severity Rating Scale (C-SSRS), for subjects 8 years and over.

5.3.5 Handling of Missing Data, Drop-outs, and Outliers

5.3.5.1 Efficacy

For the last observation carried forward (LOCF) analyses, such as “Maintenance-LOCF” analyses of percent change and responder rate, if the overall duration of the Maintenance Period is less than 8 weeks, the diary data up to the last 8 weeks during the Titration and Maintenance Periods combined will be used to calculate the seizure frequency per 28 days for Maintenance-LOCF.

For the ITT analysis, subjects with no post-baseline efficacy data will have their baseline observation carried forward.

Since data is rank transformed prior to analysis, outliers will have no effect on the primary analysis.

5.3.5.2 Safety

The algorithm on the assumptions used for imputing the missing dates for AEs is given in the programming specifications.

If the day and month are missing, events will be considered treatment-emergent if the year is equal to or after the year of the first dose date; if days are missing, events will be considered treatment-emergent if the year is after the year of the first dose, or if the year is equal to the year of the first dose date and the month is equal to or after the month of the first dose date.

For the purpose of summarizing maximum severity, if the severity of an AE is missing for a subject, then, if this subject has another AE with the same preferred term that has “severe” severity, the maximum severity of the AE will be noted as “severe”; otherwise the maximum severity will be noted as missing. Similarly, for the purpose of summarizing closest relationship, if the relationship of an AE to study drug is missing, the AE will be noted to be related if there is another related AE with the same preferred term, otherwise this relationship will be noted as missing.

For determining treatment emergent markedly abnormal lab values, a missing baseline lab value will be assumed to be of grade 0.

The algorithm to impute missing dates for concomitant medications is given in the programming specifications. No special handling of missing data is planned for the analysis of any of the other safety variables.

Data exceptions or outliers will be determined by inspection of the tables, listings, and graphs in consultation with the clinical study team. The effect of outliers on analyses may be assessed by re-analyzing the data without the outliers.

All the listings will display the original missing values.

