9.1.1 Prerandomization Phase

The Prerandomization Phase will last 4 (minimum) to 8 weeks and will include a Screening and a Baseline period. (revised per Amendment 04)

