Information regarding safety assessments in Extension A is provided in [Appendix 2](#). Information regarding safety assessments in Extension B is provided in [Appendix 4](#). (revised per Amendment 04)

ADVERSE EVENTS AND EVENTS ASSOCIATED WITH SPECIAL SITUATIONS

An AE is any untoward medical occurrence in a subject or clinical investigation subject administered an investigational product. An AE does not necessarily have a causal relationship with the medicinal product. For this study, the study drug is perampanel.

The criteria for identifying AEs are:

- Any unfavorable and unintended sign (including an abnormal laboratory finding), symptom, or disease temporally associated with the use of an investigational product, whether or not considered related to the investigational product (Note: Every sign or symptom should not be listed as a separate AE if the applicable disease [diagnosis] is being reported as an AE)
- Any new disease or exacerbation of an existing disease

- Any deterioration in nonprotocol-required measurements of a laboratory value or other clinical test (eg, ECG or x-ray) that results in symptoms, a change in treatment, or discontinuation of study drug
- Recurrence of an intermittent medical condition (eg, headache) not present pretreatment (Baseline)
- An abnormal laboratory test result should be considered an AE if the identified laboratory abnormality leads to any type of intervention, withdrawal of study drug, or withholding of study drug, whether prescribed in the protocol or not.

All AEs observed during the study will be reported on the CRF. All AEs, regardless of relationship to study drug or procedure, should be collected beginning from the time the subject signs the study ICF through the last visit in the Treatment Phase after the subject's last dose. Serious AEs will be collected for 28 days after the last dose.

Abnormal laboratory values should not be listed as separate AEs if they are considered to be part of the clinical syndrome that is being reported as an AE. It is the responsibility of the investigator to review all laboratory findings in all subjects and determine if they constitute an AE. Medical and scientific judgment should be exercised in deciding whether an isolated laboratory abnormality should be classified as an AE. Any laboratory abnormality considered to constitute an AE should be reported on the Adverse Event CRF.

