5.6.2 Adverse Events

The AE verbatim descriptions (investigator terms from the CRF) will be classified into standardized medical terminology using the Medical Dictionary for Regulatory Activities (MedDRA). Adverse events will be coded to the MedDRA (Version 24.1 or higher) lower level term (LLT) closest to the verbatim term. The linked MedDRA preferred term (PT) and primary system organ class (SOC) will also be captured in the database.

A TEAE is defined as an AE that emerged during treatment, having been absent at pre-treatment (Baseline) or

- Re-emerged during treatment, having been present at pre-treatment (Baseline) but stopped before treatment, or
- Worsened in severity during treatment relative to the pre-treatment state, when the AE was continuous.

Only those AEs that are treatment emergent will be included in summary tables. All AEs, treatment emergent or otherwise, will be presented in subject data listings.

TEAEs will be summarized by treatment group and by age group. The incidence of TEAEs will be reported as the number (percentage) of subjects with TEAEs by SOC and PT. A subject will be counted only once within a SOC and PT, even if the subject experienced more than one TEAE within a specific SOC and PT. The number (percentage) of subjects with TEAEs will also be summarized by maximum severity (mild, moderate, or severe).

The number (percentage) of subjects with TEAEs will also be summarized by relationship to study drug (related and not related). Summaries of treatment-related TEAEs will be produced.

There will also be summaries of TEAEs by dose at onset and exposure-adjusted event rates.

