8.2.2 Treatment Duration for Safety Analyses

The treatment duration for non-AE safety variables is considered to begin at or after the first dose of study drug on Day 1 and ends 14 days after the last dose of double-blind study medication. For AEs, the treatment duration is considered to begin on Day 1 and ends 28 days after the last dose of double-blind study medication.

The post-treatment duration is considered to begin on the day after the treatment duration for safety. Since it is not always possible for all study participants to come in for their clinic visits on the exact day specified in the protocol schedule, the visit week of a subject's visit will be based on the actual visit occurring during the treatment duration. These visits will be used to create by visit summaries for laboratory, and vital signs data. The end of treatment value is the last non-missing value in the treatment duration.

Any concomitant medication taken within the 14 days after the last dose data will be listed/summarized as part of the concomitant medication listing/table.

AEs for the subject were collected and reported on CRF starting from the time the subject signed informed consent to the last visit in the Treatment Phase following the subject's last dose. Serious AEs were collected for 28 days after the last dose.

For summaries of safety by time points, the time points will be relative to date of first dose. For standardized reporting, study day windows relative to the first dose (Day 1) in the study will be applied to determine into which week the data will be mapped. Scheduled, unscheduled, and early withdrawal visits will be mapped to weeks. [Table 2](#) below gives the mapping of relative day ranges to week for vital sign assessments. [Table 3](#) below gives the mapping of relative day ranges to week for laboratory assessments. If a subject did not have a recorded observation falling within a given range of days in order to be assigned to a week, the subject's data for that week will be regarded as missing for summarization purposes. If there are two or more assessments in the same window then:

- if the window is the baseline assessment, then the latest assessment will be used in the summary tables;
- if the window is the follow-up assessment, then the latest assessment will be used in the summary tables;

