5.2.5 Handling of Missing Data, Drop-outs, and Outliers

A conservative principle will be used for an AE with missing date(s) to determine if it is treatment-emergent, that is, if there are missing or partially missing AE start and/or stop dates, and it cannot be determined definitively whether an AE started during the perampanel treatment duration, it will be assumed that the AE was treatment-emergent.

If the day and month are missing, events will be considered treatment-emergent if the year is equal to or after the year of the first dose date; if days are missing, events will be considered treatment-emergent if the year is after the year of the first dose, or if the year is equal to the year of the first dose date and the month is equal to or after the month of the first dose date. A similar principle will be used for a medication with missing date(s). If there are missing or partially missing medication start and/or stop dates, and it cannot be determined definitely whether a medication was taken concomitantly with perampanel, it will be assumed that the medication is concomitant. A detailed algorithm to impute missing dates is given in the programming specifications.

For the purpose of summarizing maximum severity, if the severity of an adverse event (AE) is missing for a subject, then, if this subject has another AE with the same preferred term that has “severe” severity, the maximum severity of the AE will be noted as “severe”; otherwise the maximum severity will be noted as missing. Similarly, for the purpose of summarizing closest relationship, if the relationship of an AE to study drug is missing, the AE will be noted to be probably related if there is another probably related AE with the same preferred term, otherwise this relationship will be noted as missing.

No special handling of missing data is planned for the analysis of any of the other safety variables.

All the listings will display the original missing values.

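### The Core SAP rule for partial adverse-event dates compares only with the first dose and is not reconciled with the 28-day AE window or the TEAE definition

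*SAP*

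**What the plan says.** Four places bear on this.

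- **Core SAP 5.3.5.2 (Safety).** With day and month missing, "events will be considered treatment-emergent if the year is equal to or after the year of the first dose date". With only the day missing, an event in a later year qualifies. Within the first-dose year the test is: "if the year is equal to the year of the first dose date and the month is equal to or after the month"; the reference month is the one in which dosing began. The section also states: "The algorithm on the assumptions used for imputing the missing dates for AEs is given in the programming specifications". Those specifications are separate documents and are not available.
- **Core SAP 8.2.2.** "For AEs, the treatment duration is considered to begin on Day 1 and ends 28 days after the last dose of double-blind study medication". Protocol 9.7.1.8 also ends the TEAE period 28 days after the last dose.
- **Core SAP 5.6.2.** The definition begins: "A TEAE is defined as an AE that emerged during treatment, having been absent at pre-treatment (Baseline) or"; the two alternatives are recurrence on treatment and worsening on treatment.
- **Extension SAP 5.2.5.** An event is assumed treatment-emergent when dates are missing or partial and "it cannot be determined definitively whether an AE started during the perampanel treatment duration". The same year-and-month sentence as in the Core SAP then follows.

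On collection, Protocol 9.5.1.5 says AEs "should be collected beginning from the time the subject signs the study ICF through the last visit in the Treatment Phase". Protocol 9.1.1 adds: "The Prerandomization Phase will last 4 (minimum) to 8 weeks". Events that start and stop before dosing will therefore be in the database.

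**The concern.** Assuming that an event is treatment-emergent when its timing is unknown is ordinary caution. This rule goes further, because it also applies when the known part of the date, or the stop date, already settles the matter. The Extension SAP limits the assumption to undetermined cases. The Core SAP does not state that limit, and its 5.3.5.2 refers to neither 8.2.2 nor 5.6.2.

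The stake is the Core comparison of TEAEs between perampanel and placebo. Completers may roll straight into Extension A, where former placebo subjects start perampanel. If their later events are in the data set, a partial-date event on perampanel could be tabulated under placebo in the Core tables and again under perampanel in the Extension tables. Core exposure (5.6.1) covers Titration and Maintenance only, so an exposure-adjusted rate could count an event whose exposure time is not in the denominator. Pre-dose events would be added to both groups.

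**Working it through.** **Calendar inputs.** Protocol synopsis and 9.1: Prerandomization 4 to 8 weeks, double-blind treatment 18 weeks, Extension A 52 weeks, Follow-up 4 weeks. The protocol's own maximum reproduces: 8 + 18 + 52 + 4 = 82 weeks.

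**Windows.**
- Last Core dose: 18 × 7 = Day 126. Core AE window under 8.2.2: Day 1 to 126 + 28 = Day 154.
- Extension A dosing: Day 127 to 126 + 364 = Day 490. Adding 28 days gives Day 518.
- Days after the Core window: 518 − 154 = 364.

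**Worked example.** First dose 15 March 2018. Day 126 is 18 July 2018 and Day 154 is 15 August 2018.
- An AE dated February 2019 with the day missing: the year is later than the first-dose year, so 5.3.5.2 calls it treatment-emergent. The month alone shows that it started after 15 August 2018, during Extension A.
- An AE dated March 2018 with the day missing and a stop date of 10 March 2018: the month equals the first-dose month, so 5.3.5.2 calls it treatment-emergent. It ended five days before dosing, and 5.6.2 would exclude it.

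**How far the rule reaches.** The rule was applied day by day for 365 first-dose dates (1 January to 31 December 2018). Assumptions: the subject completes Core and Extension A, onset is uniform over time, and Extension A events are in the data.

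| Partial date | Late onsets (Days 155–518) called Core TEAEs, as written | Same, with an upper bound at Day 154 | Pre-dose onsets meeting the rule (28- or 56-day baseline) |
|---|---|---|---|
| Month known | 100% | about 4% | 52% or 26% |
| Year only | 100% | about 50% | 96% or 92% |

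The late share of all partial-date events that the rule calls Core TEAEs follows directly.
- Month known, 28-day baseline: 0.523 × 28 = 14.6 pre-dose days qualify, so 364 / (154 + 364 + 14.6) = 68%. The 56-day baseline also gives 68%.
- Year only, 28-day baseline: 0.960 × 28 = 26.9, so 364 / (154 + 364 + 26.9) = 67%.
- Year only, 56-day baseline: 0.922 × 56 = 51.6, so 364 / (154 + 364 + 51.6) = 64%.

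The upper bound loses no true Core TEAE in any of these runs. It leaves the pre-dose column unchanged; that column needs the stop-date check. The year-only events that remain are mostly ones the year cannot settle, and there the cautious assumption is reasonable.

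**Per-subject effect.** With 71 subjects per arm, one subject wrongly counted for a term adds 1/71 = 1.4 percentage points to that term's incidence. The documents do not say how many partial dates there are.

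**The case against.** The strongest reply is that no miscount has been shown. Core SAP 8.2.2 does give the AE window an end, 5.6.2 excludes events confined to the pre-treatment period, and nothing says that 5.3.5.2 overrides either. The date algorithm sits in programming specifications that may apply both limits. The Core SAP covers only the Core Study, so Extension A events may never reach its data set. The Extension SAP repeats the same lower-bound sentence beside its principle for undetermined cases, which suggests that the sponsor sees the two as compatible. All of this stands, and it limits the finding to an unreconciled rule.

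It does not remove the finding. The sentence is directive, and a programmer who applies 8.2.2 to partial dates must depart from it. Nor does the Core SAP state where Extension A events are cut off. It cites a March 2021 drug dictionary (5.2.5) for a study planned to end in about January 2020 (Protocol 9.1), so Extension A events plausibly existed when the plan was applied. That is an inference.

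A reader might infer three stronger things, which the documents do not support.
- **That events are misfiled under the randomised arm.** Core SAP 5.6 tabulates safety as treated, by treatment group.
- **That the difference between groups must narrow.** Subjects from the perampanel group also enter Extension A, and the same rule would add their late events. No net direction follows.
- **That about two thirds of Core TEAEs would be wrong.** The 64–68% concerns partial-date events only, under uniform onset and full completion of Extension A. The Extension SAP (section 7) records early termination of the study, so full completion is a ceiling.

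**Conclusion.** The concern holds as a defect of specification. Read as written, 5.3.5.2 classes two kinds of partial-date event as Core TEAEs against 5.6.2 or 8.2.2:

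1. events with a known stop date before the first dose;
2. events whose known month or year falls after the last double-blind dose plus 28 days, on condition that Extension A events are in the Core analysis data.

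For former placebo subjects, the second kind would put events on perampanel in the Core placebo column. The size is unknown, because neither the number of partial dates nor the Core data cut is given, and the direction of any bias cannot be derived. Only the safety tables are affected; the efficacy analyses are not.

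A separate matter should not be charged to this rule. Roll-over is immediate, so Days 127 to 154 on perampanel lie inside the 8.2.2 window for former placebo subjects even with complete dates. The term for double-blind medication in 8.2.2 could also be read to include the blinded Conversion Period.

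**What to change.** Keep the existing first-dose lower bound in Core SAP 5.3.5.2 and add:

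> This rule applies only when the available parts of the start and stop dates do not place the event outside the 8.2.2 treatment duration. An AE whose known stop date is before the first dose, or whose earliest possible start date is after the end of the 8.2.2 AE window, is not treatment-emergent.

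The lower bound must stay. Without it, an ongoing event that began in the month before the first dose would become a TEAE, which the present text correctly prevents.

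If the window is to be cut at the first Extension A dose for roll-over subjects, make that change in 8.2.2. Placed in 5.3.5.2, it would give partial-date events a shorter window than complete-date events.

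The cost is this short addition to the SAP and the matching lines in the programming specifications. No new data are needed.

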5.3.6 Other Considerations

Not applicable.

5.4 EFFICACY ANALYSES

5.4.1 Primary Efficacy Analyses

The primary efficacy endpoint will be the percent change from baseline in drop seizure frequency per 28 days during treatment.

A drop seizure is defined as a tonic-atonic or myoclonic with fall.

The null hypothesis and alternative hypothesis are:

H₀: perampanel is not superior to placebo in reducing drop seizure frequency

H₁: perampanel is superior to placebo in reducing drop seizure frequency

The percent change from baseline will be analyzed over the Titration and Maintenance Periods combined in the FAS. Drop seizure frequency per 28 days (as determined from subject diaries) will be calculated as the number of drop seizures divided by the number of days in the interval and multiplied by 28.

Analysis will be conducted using rank analysis of covariance (ANCOVA) with treatment, region (Asia/Pacific, Europe, North America) and age-group (2-<12 years, >=12 years) as factors, and the baseline drop seizure frequency as a covariate (Conover and Inman, 1982).

In this analysis, all drop seizure frequency data will first be rank-transformed for both baseline and endpoint drop seizure frequencies separately. The ANCOVA will then be conducted based on the rank-transformed data. Treatment effect will be tested at a 2-sided 5% level.

Due to an expected irregular distribution of drop seizure frequency, median will be the primary statistic of interest for the primary endpoint. Hodges-Lehmann estimator (Hodges and Lehmann, 1963) and 95% confidence interval (CI) for this estimator will be displayed for understanding the treatment effect size.

The following sensitivity analyses will be conducted for the endpoint of percent change in drop seizure frequency:

- Analysis on the Maintenance with LOCF to impute for missing data, and Titration period in the FAS. In the “Maintenance-LOCF” Analysis for the percent change, if a subject has less than 8 weeks of Maintenance Period, the drop seizure frequency during the last 8 weeks of the Titration and Maintenance Periods combined (or drop seizure frequency during the Titration and Maintenance Periods combined for subjects with less than 8 weeks of Titration and Maintenance Periods combined) will be used to impute for this sensitivity analysis.

A duration of 8 weeks for the missing data imputation for the percent change is meant to provide more stable estimates for the drop seizure frequency.

- Analysis of the percent change using the PP Analysis Set.
- Analysis of the percent change using the ITT Analysis Set.
- Analysis of subjects in the FAS who complete the entire study period i.e. have last scheduled double-blind visit completed and is marked by the investigator to have completed the study (Completers).

A by visit summary of percentage change will also be produced.

The following graphical displays will be produced: cumulative distribution function of percent change in drop seizure frequency during treatment, plots of median percent change from pre-randomization in drop seizure frequency by major analysis windows, by week during titration and by visit. A bubble plot of the Hodges-Lehmann median difference between perampanel and placebo by country and forest plots of percent change in drop seizure frequency by analysis windows and sub-groups will also be produced.

